2.4. Definition of Subgroups

[Table 8](#) defines subgroups of interest for investigation across several efficacy, safety, virology and other analysis endpoints (type of analysis = data domains). Refer to [Section 5](#) for a detailed overview of efficacy endpoints (primary, secondary and exploratory).

The following data handling applies to subgroup presentation:

- With the exception of Region [Class 1], subgroups will only be presented if, based on total number of subjects across treatment groups:
 - Subgroups with two strata: N = 36 in both strata
 - Subgroups with more than two strata: N = 36 in at least one stratum
 Aforementioned data handling results in approximately 12 subjects minimum per treatment group with data in a stratum. This minimum number of subjects ensures sufficient data for meaningful subgroup analysis.
- Symptom onset:
 - Cohort 1: unless otherwise specified for a given endpoint, exploratory endpoints, as detailed in [Section 5.4](#), will only be analyzed in the stratum: subjects with symptom onset ≤ 3 days before randomization. Subsequent subgroup analyses will be performed within this stratum only and also considering meaningful number of subjects as previously described.
 - In case of population enrichment decision (subjects with symptom onset ≤ 3 days before randomization), efficacy analyses will focus on those subjects with symptom onset ≤ 3 days before randomization stratum only. Subsequent subgroup analyses will be performed within this stratum only and also considering meaningful number of subjects as previously described.

- **Table 8** provides a general overview of the subgroups to be investigated per type of analysis (data domain). For any given type of analysis, subgroup presentation will not be performed for all endpoints within the given domain but will be focused on the key outputs only. For example, 2 = viral load and 3 = clinical course endpoints below, all subgroups indicated in **Table 8** will only be analyzed and presented for the primary endpoint and key clinical course endpoints (i.e. endpoints included in previous decision-making).
- Subgroup analysis and presentation may comprise tabulation of results and/or graphical presentation as best suits the purpose of the subgroup investigation. Specific details of- and format of subgroup analyses will be detailed in a separate document (data presentation specifications [DPS]) and is not included within the scope of this SAP.

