Region [Class 2]	
Based on country according to United Nations classification of geographic regions:
 
 • Asia-Oceania (APAC) • Europe and Middle East and Africa (EMEA) • North America (NA) • Latin America and the Caribbean (LATAM) 	X				X		
Baseline RSV Viral Subtype	
 • RSV A • RSV B • RSV A+B 	X	X	X	X			X
Presence of Other Respiratory Pathogens	
 • No • Yes 
Note: based on respiratory pathogens panel assays performed at baseline.
	X		X	X	X		
Presence of Other Respiratory Viruses	
 • No • Yes 
Note: based on respiratory pathogens panel assays performed at baseline.
	X		X	X	X		
Prior Use of Any Medications of Interest	
 • No prior use • Prior use of only one medication of interest 
Use of at least one of the below only:
 
 ○ Antitussives prior use only ○ Bronchodilators prior use only ○ Mucolytics prior use only ○ Inhaled corticosteroids prior use only ○ Systemic corticosteroids prior use only 
 • Prior use of 2 or more medications of interest 
Note: medications of interest include: systemic and inhaled corticosteroids, antitussives, mucolytics and bronchodilators.
	X	X	X	X	X		

KEY:**1 = Demographics + Baseline Characteristics****2 = Viral Load 3 = Clinical Course Endpoints 4 = Hospitalized Subjects****5 = Exploratory Endpoints (Efficacy)****6 = Safety****7 = Virology**

Subgroup	Definition	1	2	3	4	5	6	7
Any Use of Medications of Interest (Prior and/or Concomitant)	
 No use Use of only one medication of interest Use of at least one of the below only: 
 Any use of Antibiotics only Any use of Antitussives only Any use of Bronchodilators only Any use of Mucolytics only Any use of Inhaled corticosteroids only Any use of Systemic corticosteroids only Any use of 2 or more medications of interest Note: medications of interest include: antibiotics, systemic and inhaled corticosteroids, antitussives, mucolytics, and bronchodilators. 	X	X	X	X	X		

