4.6. Prior and Concomitant Medications

Medications taken from the date when the ICF is signed through the end of study will be summarized by cohort, by treatment group and overall, by preferred term using the World Health Organization-Drug Dictionary as frequency tables for the prior and concomitant medications separately:

1. Prior medication: medication that started before the first dose of study drug, regardless of when dosing of the medication ended.
2. Concomitant medication: medication received at or after the first dose of study drug, medication that was received before initial dosing and continued after initial dosing of study drug, or medication with missing stop date.

Medication that started before the first dose of study drug and continued after the first dose of study drug will be summarized as prior medication and separately as concomitant

medication. The part on concomitant medication will be shown by ATC class level up to level 3. If a prior/concomitant therapy record has missed components of its start and/or stop dates (time and/or day and/or month and/or year), the following actions will be taken:

1. In case of partial start or stop date/times, the concomitant therapy records will be allocated to prior/concomitant using the available partial information, without imputations.
2. In case of a completely missing start date, the prior/concomitant therapy will be considered as having started before the trial.
3. In case of a completely missing end date, the prior/concomitant therapy will be considered as ongoing at the end of the trial.

All prior and concomitant medication will be listed.

In addition, the proportion (number [n] and percentage [%]) of subjects in the ITT-i/Safety analysis set with prior-, concomitant- and any use of medications of special interest will be presented. These include antibiotics, antitussives, bronchodilators, mucolytics, inhaled and systemic corticosteroids according to the following categories:

Prior use only:

Table 13: Prior Use of Medications of Interest

PRIOR USE	NO	YES
Antitussives	No prior use	Any prior use
Bronchodilators	No prior use within the 24h before first dose of study drug	Any prior use within the 24h before first dose of study drug
Mucolytics	No prior use	Any prior use
Inhaled corticosteroids	No prior use or use to a maximum of 2 consecutive days	Prior use for a minimum of 3 consecutive days

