5.2.3. Analysis Method

Mean \log_{10} RSV RNA viral load values over time will be analyzed using a restricted maximum likelihood based repeated measures approach (MMRM). The analysis model includes fixed (discrete) effect parameters for treatment, randomization stratification factors (derived), analysis visit and treatment-by-analysis visit interaction, as well as continuous covariates for baseline \log_{10} viral load and baseline \log_{10} viral load-by-analysis visit interaction. An unstructured (co)variance structure will be used to model the within-subject errors. In case this model will not converge, the Toeplitz covariance structure will be applied. The Kenward-Roger approximation will be used to estimate the denominator degrees of freedom.

For subgroup analyses, the model will also include the subgroup variable as a covariate and the subgroup-by-treatment, subgroup-by-analysis visit and subgroup-by-analysis visit-by-treatment interactions. For details about subgroups please see Section 2.4.

A generalized MCP-Mod (1) approach at 1-sided alpha-level of 2.5% will be applied based on the estimated AUC treatment group effect and variance covariance matrix. Candidate models are given by the EMax (0.40428), Exponential (0.36411) and Linear model, with the aim to test for existence of drug-related effects. Each of the dose-response shapes in the candidate set will be tested using the corresponding contrast t-test statistic, employing a critical value derived for the maximum of the t-test statistics (based on the associated multivariate t-distribution) to ensure appropriate multiplicity correction that preserves a 1-sided 0.025 Type I error rate. A dose-response trend is established when the maximum of the t-test statistics exceeds the critical value.

MCP-Mod uses dose levels 0, 3 and 9 mg/kg which correspond to Placebo, Low and High dose respectively according to the dose/kg for age-group 3 as described in Section 1.2.

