5.3.2. Endpoint-specific analysis methods

5.3.2.1. RSV RNA Viral Load (qRT-PCR)

Log₁₀ RSV RNA Viral Load

Descriptive statistics mean (SE) graphs and median (IQR) graphs will be shown for the log₁₀ RSV RNA viral load actual values and changes from baseline by analysis visit and by treatment group. Descriptive statistics will include the number of subjects, mean, standard deviation, standard error, 95% confidence interval, median, range and interquartile range. The aforementioned will be presented by the subgroups as defined in Section 2.4.

Differences on log₁₀ RSV RNA viral load by qRT-PCR between treatment groups and by analysis visit will be determined using appropriate contrasts in a similar mixed effects model as the one used for the primary efficacy endpoint (see Section 5.2.3). The 95% 2-sided confidence intervals will be presented.

Association Between Log₁₀ RSV RNA Viral Load and Covariates/Baseline Indicators

The potential association between the log₁₀ RSV RNA viral load and the following covariates and/or baseline indicators will be explored:

- Baseline log₁₀ RSV RNA viral load
- Presence/absence of risk factors for severe RSV disease
- Days since symptom onset (0,1,2,3,4,5)
- RSV subtype
- Medications of interest:
 - ◆ Any prior/concomitant use
 - ◆ No prior/concomitant use
- Supplemental oxygen at baseline
- Presence of other respiratory pathogens at baseline
- Presence of other respiratory viruses at baseline
- Age as collected at Screening (as continuous variable)
- Overall RSV symptoms summary score (ObsRO) at baseline
- Overall RSV symptoms summary score (ClinRO) at baseline
- Region [Class 2]
- Cohort [Class 1]
- Baseline neutrophils count (as continuous variable)

To predict the change in log₁₀ RSV RNA viral load over time at Day 3, Day 5 and Day 8 based on the aforementioned set of predictor variables (covariates and/or baseline indicators), multiple regression analysis using backward stepwise elimination, will be performed initially fitting all predictor variables to identify the prognostic factors. Then

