factors are deleted one-by-one until a stopping condition is satisfied. At each step, the factor showing the smallest contribution to the model is eliminated. The parameter estimates along with the 95% 2-sided confidence limits by predictor variable will be produced. In addition, residual plots and goodness of fit measures will be evaluated, but not displayed in output. The SAS® procedure GLM SELECT (selection = backward SLS = 0.1) will be used. The procedure removes factors based on significance level and stops when all factors in the model are significant at the 0.1 level.

Predictor variables which show a strong association may further be explored as additional covariates in the primary efficacy model described in Section [5.2.3](#).

RSV RNA Viral Load AUC

A similar model as used for the primary analysis will be used for the RSV RNA viral load AUC until Day 3 and until Day 8. The differences in these AUCs for active versus placebo will be derived using appropriate contrasts for both Day 3 and Day 8 and from the same model containing all RSV RNA viral load assessments from baseline through Day 8.

Least squares mean estimates of the treatment differences, including the 95% 2-sided confidence intervals, will be presented.

For subgroup analyses, the model will also include subgroup variable as covariate, subgroup-by-treatment, subgroup-by-analysis visit and subgroup-by-analysis visit-by-treatment interactions. For details about subgroups refer to Section [2.4](#).

The individual AUCs until Day 14, derived using the trapezoidal method, will be analyzed using a generalized linear model with $AUC_{Day14/0-312h}$ as a dependent variable, treatment group and randomization stratification factors (derived) as fixed factors, and baseline \log_{10} RSV RNA viral load as fixed covariate. The differences versus placebo will be estimated using appropriate contrasts and presented with 95% 2-sided confidence intervals.

Proportion of Subjects with Undetectable RSV RNA Viral Load

The proportion of subjects within the RSV RNA viral load categories (undetectable, detectable and quantifiable) will be shown in a frequency tabulation, as well as graphically, by treatment group and analysis visit. Subjects with missing data at that analysis visit will not be counted in the denominator for the proportion. Additionally, 95% 2-sided confidence interval for each binomial proportion within the individual categories will be presented as based on the Wilson score test.

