RSV-related complications: modified definition	Any subject who experienced at least one emergent adverse event included in the list of complications below will receive code 1, subjects who did not experience any of the specified emergent adverse events will receive code 0.

Measurement	Formula
[study physician-identified complications]	
 Respiratory complications: respiratory failure, respiratory distress, apneic attacks, bronchiolitis, bronchial obstruction, pneumonia, asthmatic crisis. Infectious complications: otitis media, bacterial respiratory tract infections, sepsis; Cardiovascular complications: arrhythmia, cardiogenic shock, hemodynamic instability, congestive cardiac failure; Acid-base or electrolyte complications: metabolic acidosis (serum $\text{HCO}_3^- < 16$), metabolic alkalosis (serum $\text{HCO}_3^- > 30$) 
The final list of emergent adverse events to be considered as per modified definition of RSV-related complications, will be reviewed and documented prior to a database lock.
 
The modified definition for RSV-related complications will primarily be used as follows:
 
 from IA#3 and onwards in any decision rule that requires RSV-related complications data
Need for antibiotics related to complications associated with RSV: Investigator assessment [categorical]	
Need for antibiotics is defined as 'Yes' if the answers to the following 2 questions on the Adverse Events eCRF are answered with 'Yes' (Yes to both questions):
 
 Is this AE a complication related to the current respiratory infection? Concomitant or additional therapy given for this adverse event? 
And if the answer to the following question on the Concomitant Medications eCRF for the related medication is answered with 'Yes'.
 
 Was this medication an Antibiotic?

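### Subgroup and optional covariate analyses condition on medication taken after the first dose, which can bias supportive treatment comparisons; only pre-dose use should be used

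*SAP*

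**What the plan says.** **Timing.** SAP Section 4.6 defines concomitant medication to include "medication received at or after the first dose of study drug". On the collection window it says: "Medications taken from the date when the ICF is signed through the end of study will be summarized".

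**Subgroup route.** Table 8 in Section 2.4 has a row labelled "Any Use of Medications of Interest (Prior and/or Concomitant" with three levels: none, one, or two or more medications. It is marked for domains 1 to 5, which include viral load (2), clinical course (3), hospitalised subjects (4) and exploratory efficacy (5). Section 2.4 says that for viral load and clinical course the subgroups "will only be analyzed and presented for the primary endpoint and key clinical course endpoints". Section 5.2.3 gives the model: "For subgroup analyses, the model will also include the subgroup variable as a covariate", together with its interactions with treatment, with visit, and with both.

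**Covariate route.** Section 5.3.2.1 lists "Any prior/concomitant use" among the predictors for backward elimination, then adds: "Predictor variables which show a strong association may further be explored as additional covariates in the primary efficacy model". No sentence limits this to variables measured before dosing.

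**Reuse.** Section 5.3.2.3.2 (time to hospital discharge) and Section 5.4.2 (time to resolution, 24-hour supplementation-free definition) take the same list into AFT models with a treatment interaction.

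**Overlap with endpoints.** The medications of interest in the any-use variable include antibiotics. Table 22 in Section 5.4.1 defines an exploratory endpoint: "Need for antibiotics related to complications associated with RSV: Investigator assessment".

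**The concern.** Whether a child receives a bronchodilator, a corticosteroid or an antibiotic after the first dose depends on how the illness develops, and the trial drug is meant to change that. Splitting or adjusting by such use compares treated and placebo children who are alike on a consequence of their illness under treatment, not on a characteristic they brought to randomisation. Part of a real effect can be removed, and unmeasured severity can become unbalanced between arms within a stratum.

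The problem is sharpest for the incidence of RSV-related complications. The modified definition in Table 22 includes pneumonia, otitis media, bacterial respiratory infection and sepsis. A no-use stratum that excludes antibiotic users will tend to exclude children with those events, so the endpoint is partly stratified by itself.

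For the primary endpoint there is also a question of order. The AUC ends at Day 5, but a medication started later in follow-up, which runs to about Day 28 (Section 1.2), still assigns the child to a use stratum.

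A reader of the resulting subgroup tables or forest plots could take a difference between strata for effect modification when it is an artefact of conditioning.

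**Working it through.** **Step 1: what kind of variable it is.** The other predictors in the Section 5.3.2.1 list are baseline or screening measurements or fixed characteristics: baseline viral load, risk factors, days since onset, subtype, oxygen and co-pathogens at baseline, age at screening, baseline symptom scores, region, cohort and baseline neutrophils. Medication use is the only item that can be determined after the first dose.

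**Step 2: which analyses use it.**
- Pre-specified primary model (Section 5.2.3): no medication term.
- Sensitivity analyses (Section 5.2.3.1): none adds one.
- Interim rules (Section 5.6): full population and the subgroup with onset within 3 days; no medication term.
- Subgroup MMRM and subgroup displays (Sections 2.4, 5.2.3): planned, subject to the minimum-number rule.
- AFT association models (Sections 5.3.2.3.2, 5.4.2): planned.
- Added covariate in the primary efficacy model (Section 5.3.2.1): optional.

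**Step 3: the effect size used for scale.** Section 1.4 assumes a 20% reduction and a CV of 35%, so the standardised effect is 0.20/0.35 = 0.571 SD. As a check on this input, MCP-Mod power with 74 per arm, doses 0, 3 and 9, the stated candidate parameters and one-sided 2.5% comes to 92.6, 95.5 and 96.8% (linear, Emax, exponential). Table 1 states 92.3, 95.3 and 96.6%. The point itself does not depend on power.

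**Step 4: illustrations.** The document gives no rate of medication use and no relation between use and outcome, so every coefficient below is assumed. Each run has two arms and 400,000 subjects. T is treatment, U is unmeasured severity, e is noise, and the true effect is -0.571 SD. Attenuation is 1 - (adjusted effect / -0.571).

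*A. Treatment lowers use directly.* Y = -0.571T + 0.5U + √0.75·e; logit P(use) = 1.0U + γT; 50% use on placebo.

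| γ | Use on active | Adjusted effect (SD) | Attenuation |
|---|---|---|---|
| 0 | 50% | -0.572 | none |
| -0.3 | 44% | -0.547 | 4% |
| -0.6 | 38% | -0.525 | 8% |
| -1.0 | 30% | -0.487 | 15% |

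Effects within the use strata shift by similar amounts; at γ = -1.0 they are -0.483 and -0.489. With a true effect of zero and use of 50% against 38%, adjustment produces a spurious +0.05 SD.

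*B. Use follows the on-treatment outcome.* Y = -0.571T + e; logit P(use) = gY. For g = 0.3, 0.6 and 1.0 the adjusted effect is -0.558, -0.530 and -0.476 SD, that is 2%, 7% and 17% attenuation.

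*C. Use follows both outcome and unmeasured severity.* Y = -0.571T + √0.5·U + √0.5·e; use occurs when bY + 0.7U + noise is above its median. For b = 0.5 (use 54% v 46%) the adjusted effect is -0.49 SD; for b = 1.0 (56% v 44%) it is -0.42 SD. Attenuation is 14% and 27%, taken before rounding the effects.

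**Step 5: the same analysis with a pre-dose variable.** A variable that treatment cannot affect corresponds to γ = 0 in A. The adjusted effect is -0.572 and the stratum effects are -0.568 and -0.576, so there is no bias beyond simulation error.

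**The case against.** The strongest reply is that nothing confirmatory is touched. That stands. A reader might infer that the primary treatment effect is biased as planned, or that backward selection feeds medication use into the primary test. The SAP does not support either reading. The primary model is fixed without a medication term, the quoted sentence sits among secondary-endpoint methods, and its wording is permissive. The backward regression also lists no treatment term and aims to find prognostic factors, so that step yields no treatment comparison to bias.

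Three further objections are fair.
- The antibiotic endpoint is exploratory and limited to antibiotics for investigator-judged RSV complications, which is narrower than any antibiotic use. The overlap is real but partial.
- The 27% figure should not be read as typical. It comes from one assumed set of coefficients, and it leaves out prior use although the variable is prior and/or concomitant. If severity-related prior use in 30 to 70% of children is added (also an assumption), the 14% falls to about 10 to 4% and the 27% to about 18 to 6%. Attenuation within the no-use stratum persists.
- The SAP already plans a prior-use subgroup for the same domains and a summary of concomitant use by treatment group. According to the amendment history, medications of interest were added to look at their use and its possible impact on the PRESORS scores, which is a legitimate question.

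The planned subgroup and AFT analyses survive these objections. They direct treatment comparisons for the primary and other efficacy endpoints at strata formed after dosing, with no caveat on interpretation. A stratum defined by post-dose use cannot answer the PRESORS question either.

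**Conclusion.** The point holds for the supportive and exploratory analyses only. As written, the SAP will produce treatment comparisons conditioned on a post-randomisation variable, and it leaves open adding that variable to the primary efficacy model as an exploratory covariate. These comparisons can be biased if treatment, or an outcome it changes, affects medication use. That is plausible here because the drugs are given for the symptoms and complications under study. If treatment and those outcomes do not affect use, the illustrations show no bias.

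Neither size nor direction can be derived from the document; the range from none to about 27% attenuation rests entirely on assumed inputs. The change is worth making because a pre-dose alternative is largely in place.

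**What to change.** 1. In Section 5.3.2.1, and wherever its list is reused (Sections 5.3.2.2, 5.3.2.3.2 and 5.4.2), replace any prior/concomitant use with pre-dose use only. Add a prior-antibiotics category, because Table 13 has no antibiotics row and a plain substitution would drop prior antibiotics unnoticed.
2. State in Section 5.3.2.1 that only variables determined before the first dose may be explored as added covariates in the primary efficacy model.
3. In Table 8, remove the any-use row from the efficacy domains (2 to 5) and rely on the existing prior-use row.
4. Keep concomitant use as the descriptive summary by treatment group already planned in Section 4.6; no new table is needed.

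The cost is SAP wording, a small derivation for prior antibiotics and fewer subgroup tables. What is lost is the display of outcomes by on-study medication use.
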